Subjects in Group B2 who tolerated and effectively mobilized with plerixafor were given the option to postpone drug product manufacture until Group C opened, to allow drug product manufacture using plerixafor mobilized cells. In Group C, subjects for whom adequate HSCs are collected to achieve the minimum cell dose but not for rescue, and who do not tolerate plerixafor or do not effectively mobilize with plerixafor may be offered the option of bone marrow harvest for collection of back-up cells only, provided that drug product manufactured from mobilized cells has met criteria for dispositioning for clinical use.

As of Version 8.0 of this protocol, Group C will include adolescent subjects ≥ 12 and < 18 years of age in addition to subjects ≥ 18 and ≤ 50 years of age. It should also be noted that while all Group A subjects and some Group B subjects received drug product manufactured using “Process 1”, all current and future Group C subjects will receive drug product manufactured using an optimized process termed “Process 2”. Treatment with drug product manufactured using Process 2 (versus Process 1) has resulted in increased drug product VCN, peripheral blood VCN, and HbA^{T87Q} levels across multiple bluebird bio-sponsored clinical studies.

The drug product must be release tested and dispositioned for clinical use and stored at the study site before the subject can begin myeloablative conditioning with busulfan.

Stage 3 –Myeloablative conditioning and infusion of bb1111

The subject’s suitability for transplant will be reconfirmed with clinical laboratory tests (complete blood count [CBC], serum chemistry, liver function tests, and pregnancy test), physical examination, performance status, cytogenetics, and other tests based on institutional requirements. The results of these tests will be reviewed, and availability of the drug product on site and the availability of back-up cells will be confirmed before the site can proceed with conditioning.

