1.2. Study Design

1.2.1. Synopsis of Study Design

This is a non-randomized, open label, multi-site, single dose, Phase 1/2 study in approximately 50 adults and adolescents with severe SCD. The study will evaluate the efficacy and safety of autologous hematopoietic stem cell transplantation (HSCT) using bb1111 (lovotibeglogene autotemcel, also known as LentiGlobin BB305 Drug Product for SCD), an autologous CD34+ cell-enriched population from patients with SCD that contains hematopoietic stem cells (HSCs) transduced with BB305 lentiviral vector encoding the β^{A-T87Q} -globin gene, suspended in cryopreservation solution.

The study has 4 distinct stages, as follows:

Stage 1 - Screening and eligibility assessment

Stage 2 - Stem cell harvest, drug product manufacture and disposition

Stage 3 - Myeloablative conditioning and drug product infusion

Stage 4 - Follow-up for approximately 24 months after drug product infusion

Subjects are placed into 1 of 3 non-randomly assigned Groups (Groups A, B, or C), depending on the date of informed consent and the method of stem cell collection for either rescue or drug

product manufacture. The detailed definition of the Groups can be found in study Protocol HGB-206 Section 5.3, and the main differences among these Groups are listed in [Table 1](#).

Table 1. Study Design and Selected Details for Groups A, B and C

	Group A	Group B1	Group B2	Group C
Number of subjects consented and originally assigned to this group	9	1	3	51
Number of subjects received drug product infusion in this group	7	1	1	36
Number of subjects reassigned to Group C before drug product infusion	0	0	2	NA
Method of stem cell collection				
For drug product	BMH	BMH	BMH	Mobilization/Apheresis
For back-up cells	BMH	BMH	Mobilization/Apheresis	Mobilization/Apheresis
Drug product manufacturing process	Process 1	Process 1 & Process 2	Process 2	Process 2a

BMH= bone marrow harvest; NA = not applicable

- Group A: Nine subjects who consented and had bone marrow harvested for stem cell collection were retrospectively assigned to Group A. Two of 9 withdrew from the study before initiating conditioning and did not receive drug product infusion. Seven of the 9 subjects received drug product infusion, and both drug product and back-up cells were derived from bone marrow harvest. All drug products were manufactured using Process 1.

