4.4.5. Analysis of Correlation

The following exploratory correlation analyses, but may not be limited to, will be conducted:

- VOE-CR (Yes or No) (in TPVOE for Group C and Overall) versus:
 - Globin Response (Yes or No)
 - VOE-CR24 (Yes or No)
 - sVOE-CR24 (Yes or No)
 - non-transfused HbA^{T87Q} (% of non-transfused total Hb) at Month 6
 - DP VCN (c/dg)
 - DP %LVV+ cells
 - Total CD34+ cells (10⁶/kg) infused
 - PB VCN (c/dg) at Month 6
 - PB %LVV+ cells at Month 6
- sVOE-CR (Yes or No) (in TPVOE for Group C and Overall) versus:
 - Globin Response (Yes or No)
 - sVOE-CR24 (Yes or No)
 - non-transfused HbA^{T87Q} (% of non-transfused total Hb) at Month 6
 - DP VCN (c/dg)
 - DP %LVV+ cells
 - Total CD34+ cells (10⁶/kg) infused
 - PB VCN (c/dg) at Month 6
 - PB %LVV+ cells at Month 6
- Globin response (Yes or No) (in TP for Group C and Overall) versus:
 - VOE-CR24 (Yes or No)
 - sVOE-CR24 (Yes or No)
 - non-transfused HbA^{T87Q} (% of non-transfused total Hb) at Month 6
 - DP VCN (c/dg)
 - DP %LVV+ cells
 - Total CD34+ cells (10⁶/kg) infused
 - PB VCN (c/dg) at Month 6
 - PB %LVV+ cells at Month 6
- HbA^{T87Q} (% of non-transfused total Hb in TP for Group C and Overall) at Month 6 versus:
 - Change (%) from baseline in annualized number of adjudicated sVOEs
 - Change (%) from baseline in annualized number of adjudicated VOEs

- DP VCN (c/dg)
- DP %LVV+ cells
- Total CD34+ cells ($10^6/\text{kg}$) infused
- PB VCN (c/dg) at Month 6
- PB %LVV+ Cells at Month 6
- HbS (% of non-transfused total Hb) at Month 6

Scatter plots for DP VCN (c/dg) and DP %LVV+ Cells versus HbA^{T87Q} (% of non-transfused total Hb) at Month 6 for TP Group C and Overall will be provided to explore whether there is a positive correlation trend between these drug product characteristics and HbA^{T87Q} (%) at Month 6. For this analysis, data may be transformed as appropriate.

- Non-HbS (% of non-transfused total Hb in TP for Group C and Overall) at Month 6 versus:
 - Change (%) from baseline in annualized number of adjudicated sVOEs
 - Change (%) from baseline in annualized number of adjudicated VOEs
- HbA^{T87Q} (% of non-transfused total Hb in TP for Group C and Overall) at Month 6 versus:
 - Change from baseline in total bilirubin at Month 6
 - Change from baseline in indirect bilirubin at Month 6
 - Change from baseline in lactate dehydrogenase at Month 6
 - Change from baseline in reticulocytes at Month 6

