4.5. Pharmacodynamic Analysis and Correlation Analysis

Analyses will be conducted using the TP and SEP (if different than TP), or subgroups of TP as applicable, and will include summary tables with descriptive statistics and figures (all values versus time on x-axis), and displaying the items below:

- PB VCN over time will be summarized per time point, and by-subject spaghetti plots presented. Bone marrow and lineage cells VCN will be included in a listing only, if available.
- By-subject over time summaries and spaghetti plots for Group C will also be presented for exploratory analyses:
 - %LVV+ colonies over time
 - % β^{A-T87Q} + RBCs over time
- The following exploratory correlation analyses plots, but may not be limited to, will be conducted in TP:
 - Weighted average DP %LVV+ Cells vs weighted average DP VCN (TP overall)
 - PB VCN at Month 6 vs weighted average DP VCN (TP Group C)
- Hemoglobin fractions (including HbA^{T87Q}, HbA, HbA₂, HbS and HbF, as relevant, calculated using ratio data from HPLC and total Hb) are summarized by time point. Additionally, each fraction over time will be presented in a by-subject spaghetti plots separately for all subjects in TP. The ratios and total Hb used to derive the fractions will also be included in a by-subject listing.
 - HbA^{T87Q} = β^{A-T87Q} -Globin to All β -Like-Globin-Chains/100×total Hb
 - HbA = β^A -Globin to All β -Like-Globin-Chains/100×total Hb
 - HbA₂ = δ -Globin to All β -Like-Globin-Chains/100×total Hb
 - HbS = β^S -Globin to All β -Like-Globin-Chains/100×total Hb
 - HbF = (γ G-Globin to All β -Like-Globin-Chains + γ A-Globin to All β -Like-Globin-Chains)/100×total Hb
 - Ratio of α -globin to total of all β -like globins if data available

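### The pooled Overall correlations of DP VCN and PB VCN with Month 6 HbA-T87Q mix manufacturing process and cell source with any within-process relation, and can be inflated (minor, exploratory).

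*Protocol*

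**What the plan says.** Protocol 3.1 (Overall Design and Plan of the Study), repeated in the synopsis, reports a process effect: "Treatment with drug product manufactured using Process 2 (versus Process 1) has resulted in increased drug product VCN, peripheral blood VCN". The same sentence adds HbA-T87Q and attributes the finding to several of the sponsor's studies.

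SAP 1.2.1 and its Table 1 tie process to group and to cell source:

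- **Group A:** 7 treated subjects, marrow source. "All drug products were manufactured using Process 1".
- **Group B1:** 1 subject, marrow source, one Process 1 lot and one Process 2 lot.
- **Group B2:** 1 subject, marrow source, both lots Process 2.
- **Group C:** 36 treated subjects, apheresis source, Process 2a.

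SAP 4.4.5 (Analysis of Correlation) sets Month 6 HbA-T87Q, as a percentage "of non-transfused total Hb in TP for Group C and Overall) at Month 6 versus", against DP VCN, DP %LVV+ cells, CD34+ dose and Month 6 PB VCN, among others. Scatter plots of DP VCN and DP %LVV+ against HbA-T87Q "for TP Group C and Overall will be provided to explore whether there is a positive correlation trend between these drug product characteristics" and HbA-T87Q. The responder endpoints are handled in the same two sets, for example "VOE-CR (Yes or No) (in TPVOE for Group C and Overall) versus" and "Globin response (Yes or No) (in TP for Group C and Overall) versus". Pairs of continuous variables get a Pearson coefficient, and a continuous variable against a binary one gets a Mann-Whitney test.

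No stratification by process or group is described. SAP 3.6 plans no covariate adjustment, and SAP 3.8 does not list process as a subgroup.

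SAP 4.5 plots one pair in the pooled set only: "Weighted average DP %LVV+ Cells vs weighted average DP VCN (TP overall". The plot listed next, PB VCN against DP VCN, is limited to Group C.

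**The concern.** If two variables are both higher in one subgroup than in another, they correlate when the subgroups are pooled, even with no relation inside either. The protocol reports such a joint rise for DP VCN, PB VCN and HbA-T87Q, in the direction the scatter plots look for. The data transformation that SAP 4.4.5 allows would not remove a shift between groups.

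At stake is how the Overall column is read. These analyses ask whether product characteristics track HbA-T87Q. In the Overall set, a positive coefficient could reflect VCN itself, something else that changed with the process, or the move from marrow to apheresis. The unadjusted value does not say which.

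**Working it through.** **Stated figure.** The plan gives no coefficient, sample size or power for these correlations, so there is no figure to reproduce.

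**Inputs.**
- Treated subjects (SAP Table 1): 7 + 1 + 1 + 36 = 45.
- Process 1 subjects: 7 (Group A). The mixed-lot B1 subject and the Process 2 B2 subject are counted on the newer-process side. This is the lower of the two splits shown.
- Direction of the shift: upward in both variables (Protocol 3.1). The protocol calls Group C's process Process 2, while SAP Table 1 calls it Process 2a. I treat the statement as applying to Group C.
- Size of the shift, d, in within-process SDs: **assumption, not in the documents**. The range is 0.5 to 3, equal in both variables.
- Within-process correlation: set to zero, to isolate what pooling alone produces.
- All 45 subjects are assumed to have both values at Month 6.

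**Formula.** For a two-group mixture with Process 1 share π and v = π(1 − π):

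r = v·d² / (1 + v·d²)

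Here v = (7/45)(38/45) = 266/2025 = 0.1314. At d = 2, v·d² = 0.525 and r = 0.525/1.525 = 0.34.

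**Results.** Rejection rates come from 20,000 simulated data sets per row, with a two-sided Pearson test at 0.05. The SAP sets no such threshold for these coefficients, so it serves only as a yardstick.

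| d (SD) | Expected pooled r | Chance of p<0.05 |
|---|---|---|
| 0.5 | 0.03 | 5% |
| 1 | 0.12 | 12% |
| 1.5 | 0.23 | 33% |
| 2 | 0.34 | 68% |
| 3 | 0.54 | 99% |

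**Sensitivity to the split.** If both Group B subjects are placed with Group A (9 versus 36), v = 0.2 × 0.8 = 0.16. At d = 2, r = 0.64/1.64 = 0.39, and the chance is 81%.

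**Both variables must shift.** With a 2 SD shift in one variable and none in the other, the pooled r is 0.00 and the rejection rate is 5%.

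**What adjustment does.** In the newer-process subjects alone, or with a partial correlation adjusted for the same split that carries the shift, the mean r is 0.00 and the rejection rate about 5% at every d.

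The practical adjustment, A/B versus C, is close to this but not perfect if the two Group B subjects sit at the newer-process level. Seven low and two high values then remain in one stratum. They add (7 × 2/9)d² = 1.556d² to the within-stratum cross-product, against 43 residual degrees of freedom. The expected partial r is about 1.556d²/(43 + 1.556d²). That is 1.556/44.556 = 0.03 at d = 1 and 6.22/49.22 = 0.13 at d = 2, against 0.12 and 0.34 unadjusted. Most of the artefact goes, and some can remain at large shifts.

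**The case against.** Several counter-arguments stand.

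- **The clean analysis is already planned.** Every correlation in SAP 4.4.5 is specified for Group C as well, and SAP 3.5 says efficacy analyses focus on that group. Nothing gives the Overall result priority. A reader might infer that Overall will be quoted in place of Group C, but the documents do not say so.
- **Nothing is decided here.** The analyses are labelled exploratory and feed no success criterion. The protocol's own correlation list (7.4.4.5) contains no drug-product characteristic.
- **The between-process contrast may be partly real.** If the newer process raised HbA-T87Q through higher VCN, that contrast is part of the signal, and adjusting for group removes some of it. It would therefore be too strong to say that pooling manufactures a correlation with nothing behind it. The documents cannot tell the two explanations apart.
- **The evidence is narrow.** A reader might extend the point to %LVV+, CD34+ dose, VOE-CR, sVOE-CR and Globin Response. No process shift is documented for any of these, and with a shift in only one variable the artefact vanishes. The number of Group A and B subjects in TPVOE is not given either, so nothing was computed for the two VOE endpoints.
- **The size is unknown.** At 0.5 SD the effect is negligible.

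These arguments limit the weight of the point. They do not make the unadjusted Overall coefficient interpretable, because process and cell source change together with group and the SAP does not say so.

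**Conclusion.** The point holds as a minor one, for DP VCN and PB VCN against Month 6 HbA-T87Q in the Overall set. There the unadjusted coefficient mixes a documented process shift, and a change of cell source, with any within-process relation, and it can be inflated. The artefact is negligible at a shift of 0.5 SD, material from about 1.5 SD (expected r 0.23, 33% nominal significance) and large at 2 SD or more. These figures assume zero within-process correlation, equal shifts in both variables, equal within-process SDs and complete data on 45 subjects. The true shift has to come from the data.

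The documents do not support a claim that the Overall correlations are spurious. The primary and key secondary analyses are unaffected, and so are the Group C correlations.

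**What to change.** In SAP 4.4.5 and 4.5:

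1. Name Group C as the main set for correlations that involve drug product or PB VCN.
2. Beside any Overall Pearson coefficient, report a partial correlation adjusted for group (A/B versus C). State that the unadjusted value mixes process and cell source.
3. Mark Groups A, B and C with different symbols on every Overall scatter plot.
4. Show the DP %LVV+ against DP VCN plot for Group C as well as Overall.

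Dropping Overall altogether is not needed. A stratified rank test for the binary endpoints would add little beyond Group C, with groups of 7, 1, 1 and 36.

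The cost is SAP wording, one adjustment term and a few extra outputs, with no new data. The adjusted coefficient may be smaller and may remove some true between-process VCN signal, which is why both values should be shown.

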3.2. Data Monitoring Committee

An independent Data Monitoring Committee (DMC) comprised of members with appropriate scientific and medical expertise to monitor the safety of subjects participating in the study will be convened before the study is opened. The DMC will make recommendations regarding study conduct (including stopping enrollment), but the ultimate decision is with the Sponsor. The composition, responsibilities, and meeting frequencies of the DMC will be described in the DMC charter.

Prior to myeloablative conditioning and subsequent infusion of drug product of the second subject in Group A, the DMC reviewed the safety data from the first subject treated after that subject had engrafted. The second subject was not enrolled into Group A until the DMC had determined that there were no safety concerns with the first subject. Thereafter, subject enrollment proceeded in parallel and the DMC reviewed safety data during their regular meetings.

During safety evaluation of plerixafor in Group B2, dosing of initial subjects was staggered. The DMC reviewed the AE profile during plerixafor treatment in mobilization cycle 1 for initial subjects, and evaluated on any issues of potential safety significance that could have affected determination of DLT and plerixafor dose before subsequent subjects were dosed with plerixafor (see also [Section 5.2.3](#)).

The first 2 subjects in Group C were infused with drug product in a staggered fashion: neutrophil engraftment was required to occur in the first subject treated in Group C before busulfan conditioning was initiated for the second subject.

3.3. Event Adjudication Committee

An independent Event Adjudication Committee comprised of members with appropriate scientific and medical expertise to review subject source documents will be convened during Group C. The Event Adjudication Committee will be responsible for adjudication of all investigator reported VOEs, irrespective of the severity, duration, or need for medical facility visit. The committee will review events that occurred prior to enrollment (retrospectively) as well as during the study for Groups A, B, and C. The committee may also be responsible for the adjudication of any subject deaths that occur after drug product infusion.

A charter describing the composition and conduct of this committee will be issued by the Sponsor and agreed to by all members prior to conducting any reviews.

3.4. Engraftment Failure

Neutrophil engraftment failure is defined as failure to achieve 3 consecutive ANC laboratory values $\geq 0.5 \times 10^9$ cells/L obtained on different days after the initial post-infusion nadir by Day 43, or receiving back-up cells at any time during the neutropenic phase, and is reported as an SAE (see [Section 6.2.30.2](#)).

3.5. Treatment Discontinuation and Enrollment Suspension Criteria

3.5.1. Stopping Rules for Plerixafor

Once mobilization with plerixafor has begun, there are no protocol-defined stopping rules for plerixafor. Mobilization with plerixafor followed by apheresis was introduced under Protocol HGB-206 Amendment 7.0. A plerixafor dose of 0.24 mg/kg was identified as having an acceptable safety profile by the DMC, and dose-limiting toxicities (DLTs) were no longer being assessed as of Protocol HGB-206, Amendment 8.0.

3.5.2. Stopping Rules for Busulfan

The drug product must be release tested and dispositioned for clinical use and stored at the study site, and a sufficient number of back-up cells must have been collected and stored at the study site before the subject can begin myeloablative conditioning with busulfan.

Once myeloablation with busulfan has begun, there are no protocol-defined stopping rules for busulfan. In the anticipated very rare event of consent withdrawal during conditioning or the development of a new medical condition that, in the Investigator's opinion, puts the subject at risk with continued busulfan treatment, the Medical Monitor should be contacted immediately. In such situations in which busulfan conditioning has not been completed per protocol, the drug product should not be given, and it is likely that rescue with back-up cells will be required.

3.5.3. Stopping Rules for bb1111

bb1111 is given as a single IV infusion; once the infusion has been given, there are no protocol-defined stopping rules for treatment of individual subjects.

Drug product infusion for an individual subject will not be initiated if:

- the drug product fails to meet criteria for dispositioning for clinical use. The Investigator, in consultation with the subject, may decide to proceed with an additional stem cell collection, with the approval of the Medical Monitor.

3.5.4. Enrollment Suspension Criteria

Enrollment in this study and other study procedures may be temporarily suspended at any time for safety reasons.

Following any of the events listed below occurring in a subject treated with bb1111 in a bluebird bio-sponsored clinical study, the Sponsor will convene an urgent safety review meeting to determine if enrollment (and other study procedures) in this study should be temporarily suspended, inform the DMC chair of the event, and convene an ad hoc DMC meeting as appropriate:

- Death
- Report of a hematologic malignancy (e.g., leukemia, lymphoma, myelodysplastic syndrome, or other hematologic malignancies)
- Detection of vector-derived RCL in any subject (confirmed on co-culture assay)
- Failure to achieve hematopoietic reconstitution with transduced cells requiring use of back-up cells

Subjects who have already been treated with drug product will continue in the study.

The Sponsor will inform the regulatory authorities, Investigators, and each site's Institutional Review Board (IRB)/ Independent Ethics Committee (IEC) and other appropriate institutional regulatory authorities if a decision to temporarily suspend enrollment is made.

4. STUDY POPULATION

4.1. Number of Subjects

A total of approximately 50 subjects will be treated with bb1111 in Study HGB-206.

Seven subjects have already been treated in Group A, and 2 subjects have been treated in Group B. A total of approximately 41 subjects in Group C (including subjects consented under Versions 7.0, 8.0, and 9.0 of this protocol) will be treated with bb1111, approximately 35 of which must meet the severe VOE criteria as set forth in Inclusion Criterion #3.1.

Subjects who withdraw prior to drug product infusion may be replaced.

4.2. Inclusion Criteria

Subjects must:

1. Be ≥ 12 and ≤ 50 years of age at time of consent.
2. Have a diagnosis of SCD, with either β^S/β^S or β^S/β^0 or β^S/β^+ genotype.
3. Previous Inclusion Criterion #3 is no longer applicable and has been replaced with Criterion #3.1.
 - 3.1. In the setting of appropriate supportive care measures (e.g., pain management plan) have experienced **at least 4 severe VOEs in the 24 months prior to informed consent as defined below**.

For the purposes of this study, a severe VOE is defined as an event with no medically determined cause other than a vaso-occlusion, requiring a ≥ 24 -hour hospital or emergency room (ER) observation unit visit or at least 2 visits to a day unit or ER over 72 hours with both visits requiring intravenous treatment. Exception: priapism does not require hospital admission but does require a medical facility visit; 4 priapism episodes that require a visit to a medical facility (without inpatient admission) are sufficient to meet criterion. Severe VOEs include:

- a. an episode of acute pain with no medically determined cause other than a VOE
- b. Acute chest syndrome (ACS), defined by an acute event with pneumonia-like symptoms (e.g., chest pain, fever [$> 38.5^{\circ}\text{C}$], tachypnea, wheezing or cough, or findings upon lung auscultation) and the presence of a new pulmonary infiltrate consistent with ACS and requiring oxygen treatment and/or blood transfusion.
- c. Acute hepatic sequestration, defined by a sudden increase in liver size associated with pain in the right upper quadrant, abnormal results of liver-function test not due to biliary tract disease, and reduction in Hb concentration by at least 2 g/dL below the baseline value
- d. Acute splenic sequestration, defined as sudden enlargement of the spleen and reduction in Hb concentration by at least 2 g/dL below the baseline value.
- e. Acute priapism: defined as a sustained, unwanted painful erection lasting more than 2 hours and requiring care at a medical facility (with or without hospitalization)

4. Previous Inclusion Criterion #4 is no longer applicable as of Protocol Amendment 8.0.

5. Have a Karnofsky performance status of ≥ 60 (≥ 16 years of age) or a Lansky performance status of ≥ 60 (< 16 years of age).
6. Previous Inclusion Criterion #6 is no longer applicable as of Protocol Amendment 8.0.
7. Have either experienced HU failure at any point in the past (defined as > 1 VOE or ≥ 1 ACS after HU has been prescribed for at least 6 months) or must have intolerance to HU (intolerance is defined as the patient being unable to continue to take HU per PI judgment).
8. Be treated and followed for at least the past 24 months prior to Informed Consent in medical center(s) that maintained detailed records on sickle cell disease history, including incidence of VOEs and severe VOEs, aplastic crises, infectious complications, SCD-related chronic complications, SCD-related surgery, neurovascular evaluation (including MRI/A and TCD), pRBC transfusions (including indications, volume and units of pRBCs, associated pre-transfusion HbS and total Hb values and post-transfusion AEs [including allo-immunization]), SCD-specific treatment history (e.g., HU, L-glutamine, iron overload, and chelation history), and use of pain medication.

